Subject Diary	D	C/R/D	R	C/R/D	C/R	C/R	
Study Medication	D b	C/R/D	R	C/R/D	C/R/D	C/R	
Daily Diary Completion		-----X-----					
Concomitant Medication	X a	-----X-----					
Adverse Events	X a	-----X-----					
Adverse events of special interest	X a	-----X-----					X m

AED=antiepileptic drug; BMI=body mass index; BRIEF=Behavior Rating Inventory of Executive Function; C=Collect; CBD=cannabidiol; CGI-I=Clinical Global Impression-Improvement; D=Dispense; ECG=electrocardiogram; EOS=end of study; ET=early termination; EQ-5D-5L=standardized measure of health status; HADS=Hospital Anxiety and Depression Scale; PedsQL=Pediatric Quality of Life Inventory; QoL=quality of life; QOLCE=Quality of Life in Childhood Epilepsy; R=Review

**NOTE: If a subject has a birthday during the study that makes a previously unrequired assessment now required (eg, Tanner staging in a male subject who turns 8 years old during the study), this assessment(s) should be initiated at visits subsequent to the birthday.**

**\*\* de Novo subjects are subjects who did not participate in one of the core studies and may or may not be currently taking STP.**

- a: For subjects enrolling from one of the core studies use data collected at Visit 12 and Visit 13 of Study ZX008-1501 or ZX008-1502. For de novo subjects, a screening period up to 28 days is required. During this period, informed consent is required prior to any study-related procedures. All results to determine eligibility must be reviewed prior to receiving the first dose of study medication at Visit 1. For all subjects, clinical laboratory results and all ECHO/ECG results must be available and meet eligibility criteria prior to receiving the first dose of study medication at Visit 1.
- b: De Novo subjects must meet entry criteria 3 to 7, and 10, including having had ≥4 convulsive seizures (tonic, tonic-atonic, tonic-clonic, clonic) per 4-week period for past 12 weeks prior to screening, by parent/guardian report to investigator or investigator medical notes.
- c: At the discretion of the investigator, Visit 2 may be conducted as a phone visit.
- d: Or early termination.
- e: Follow-up ECG, ECHO, and physical examination will be performed 3 and 6 months after study completion or early termination (see Section 6.3).

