  - a. Onset of seizures in the first year of life in an otherwise healthy infant.

- b. A history of seizures that are either generalized tonic-clonic or unilateral clonic or bilateral clonic, and are prolonged.
  - c. Initial development is normal.
  - d. History of normal brain MRI without cortical brain malformation.
  - e. Lack of alternative diagnosis.
  - f. Meets one of the following 3 confirmatory diagnostic criteria:
    - i. Emergence of another seizure type, including myoclonic, generalized tonic-clonic, tonic, atonic, absence and/or focal has developed after the first seizure type.
    - ii. Prolonged exposure to warm temperatures induces seizures and/or seizures are associated with fevers due to illness or vaccines, hot baths, high levels of activity and sudden temperature changes and/or seizures are induced by strong natural and/or fluorescent lighting, as well as certain visual patterns.
    - iii. Genetic test results consistent with a diagnosis of Dravet syndrome (pathogenic, likely pathogenic, variant of unknown significance, or inconclusive but unlikely to support an alternative diagnosis.)
  - g. Subject has been approved for study inclusion by the Epilepsy Study Consortium.
  - h. Subject does not have an exclusionary cardiovascular or cardiopulmonary abnormality based on ECHO, ECG or physical examination and is approved for entry by the central cardiac reader. Exclusionary abnormalities include, but are not limited to:
    - i. Mild or greater mitral or aortic valve regurgitation in subjects >18 yrs of age
    - ii. Possible signs of pulmonary hypertension with abnormal or greater than upper limit of normal values
    - iii. Evidence of diastolic dysfunction
  - i. Subject must have had  $\geq 4$  convulsive seizures (tonic, tonic-atonic, tonic-clonic, clonic) per 4-week period for past 12 weeks prior to screening, by parent/guardian report to investigator or investigator medical notes.
  - j. All medications or interventions for epilepsy (including ketogenic diet [KD] and vagal nerve stimulation [VNS]) must be stable for at least 4 weeks prior to screening and are expected to remain stable throughout the study.
11. Subject's parent/caregiver is willing and able to be compliant with diary completion, visit schedule and study drug accountability.

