### 5.6 PRIOR AND CONCOMITANT MEDICATION

All prior and concomitant medication will be collected in the CRF.

All medications taken by a subject after the first administration of IMP are regarded as concomitant medication and must be documented in the CRF, including over-the-counter medication, herbal and vitamin/supplement preparations.

Subjects are required to take at least one concomitant AED throughout the study. During at least the first 6 months of the study, subjects will continue to receive their existing AEDs at the same dose as prior to initiating this study. However, once the subject has been stable on a ZX008 dose for at least 6 months with good seizure control, investigators will be allowed as per typical clinical practice to alter one or more other concomitant AED doses as deemed clinically appropriate. Concomitant AEDs may be withdrawn completely but all subjects must remain on a minimum of 1 concomitant AED plus ZX008. No new concomitant AEDs may be introduced while in this study. All medication dose changes must be documented with a clinical explanation and justification. Concomitant AED dose adjustments outside of these parameters should be discussed with the Medical Monitor prior to initiation.

Non-study medications and therapies that are considered necessary for the subject's welfare and will not interfere with the response to the study medication may be given at the discretion of the investigator, informing the Medical Monitor as soon as possible.

It should be noted for any subject receiving hypoglycemic agents, the investigator should consider diabetic medication changes in the setting of weight loss and hypoglycemia.

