### 5.6.1 Vagal Nerve Stimulation

Subjects receiving treatment with vagal nerve stimulation (VNS) may be included as long as the VNS has been in place for at least 6 months prior to entry into the core study, or for de novo subjects prior to first dose in the OLE, and stimulation parameters have been kept constant for 4 weeks prior to core study Visit 1. During at least the first 6 months of the study, VNS stimulation parameters will be kept constant. However, once the subject has been stable on a ZX008 dose for at least 6 months with good seizure control, investigators will be allowed as per typical clinical practice to alter VNS stimulation parameters as deemed clinically appropriate. All VNS stimulation parameter changes must be documented with a clinical explanation and justification. VNS stimulation parameter adjustments outside of these boundaries should be discussed with the Medical Monitor prior to initiation. The subject's use of VNS will be recorded in the CRF.

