### 5.6.2 Ketogenic Diet

Adherence to the KD, or a modified version of KD, is permitted during the study if the dietary habits were initiated more than 4 weeks prior to entry into the core study, or for de novo subjects 4 weeks prior to first dose in the OLE. During at least the first 6 months of the study, the KD will be adhered to. However, once the subject has been stable on a ZX008 dose for at least 6 months with good seizure control, investigators will be allowed as per typical clinical practice to alter the KD as deemed clinically appropriate. All KD changes must be documented with a clinical explanation and justification. KD adjustments outside of these parameters should be discussed with the Medical Monitor prior to initiation. The subject's use of KD will be recorded in the CRF.

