### 10.5.2 Effectiveness Analyses

#### 10.5.2.1 Key Effectiveness Analysis

The key effectiveness endpoint is the change in the convulsive seizure frequency per 28 days between the pre-ZX008 Baseline and OLE Treatment Period. The frequency of convulsive seizures during a given period will be derived from the number and type of events recorded in subject diaries. The seizure frequency per 28 days will be calculated as the number of seizures recorded divided by the number of days in the period and multiplied by 28. The convulsive

seizure frequency will be calculated from all available data collected during either the pre-ZX008 Baseline or OLE Treatment Periods.

Both the mean and median frequency of convulsive seizures will be presented for the pre-ZX008 Baseline Period and the OLE Treatment Period. The significance of the change between periods will be assessed using an analysis of covariance (ANCOVA) model with age group (< 6 years, ≥ 6 years) as a factor and with pre-ZX008 baseline frequency as a covariate. Other factors may be included in the model if they are found to be informative during analyses of the core studies.

Since the ANCOVA relies on assumptions of normality, the key effectiveness endpoint will also be analyzed using a nonparametric method that does not require as stringent assumptions. A test such as the stratified Wilcoxon signed rank test will be used to assess the change from baseline while stratifying by age group.

An additional analysis will be performed to assess the sensitivity of the key effectiveness analysis to changes in dose or type of concomitant AED medications that may occur during the course of the trial. Specifically, the analysis will be repeated with a factor added to the model to indicate whether a subject had a change in prescribed dose or type of concomitant AED medication during the OLE Treatment Period. Further exploratory analyses may be conducted if changes in concomitant AED medication appear to have a significant impact on the effectiveness of ZX008.

Only subjects from Studies ZX008-1501, ZX008-1502, and Cohort 2 of ZX008-1504 will be included in change from baseline analyses of effectiveness. Subjects from Study ZX008-1504 Cohort 1 will be excluded from such analyses since they will enter the OLE Treatment Period without first participating in a baseline period that includes a formal assessment of pre-ZX008 seizure frequency.

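### The sensitivity analysis for background therapy counts only AED changes, so a subject whose only change is in vagal nerve stimulation or ketogenic diet is grouped as unchanged

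*Protocol*

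**What the plan says.** Section 10.5.2.1 states the aim of the extra analysis, to "assess the sensitivity of the key effectiveness analysis to changes in dose or type of concomitant AED medications", and then fixes its form. The key model is repeated with a factor showing "whether a subject had a change in prescribed dose or type of concomitant AED medication during the OLE Treatment Period". The optional follow-on work has the same scope: "Further exploratory analyses may be conducted if changes in concomitant AED medication appear to have a significant impact".

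Three background therapies may change during the trial. For drugs, Section 5.6 lets investigators "alter one or more other concomitant AED doses as deemed clinically appropriate". For the device, Section 5.6.1 says that "investigators will be allowed as per typical clinical practice to alter VNS stimulation parameters as deemed clinically appropriate". For the diet, Section 5.6.2 says that "investigators will be allowed as per typical clinical practice to alter the KD as deemed clinically appropriate". Section 10.5.2 mentions neither VNS nor KD.

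The legend of Table 1 gives "AED=antiepileptic drug". Inclusion criterion 10j in Section 4.1, which applies to de novo subjects, groups all three as epilepsy treatment: "All medications or interventions for epilepsy (including ketogenic diet [KD] and vagal nerve stimulation [VNS]) must be stable".

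**The concern.** The key effectiveness endpoint uses all available diary data from the OLE Treatment Period, planned at 36 months (Sections 10.4 and 10.5.2.1), so seizures recorded after a change in background therapy count towards it. All subjects form one treatment group (Section 10.3), and no concurrent control shows what a change in other therapy does by itself. The added factor is the only specified means of asking whether the result depends on such changes.

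If the factor tracks one of the three therapies, the group it calls unchanged can include subjects whose epilepsy therapy did change. At stake is how cleanly the comparison of changed with unchanged subjects can be read. The main estimate is not at stake.

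**Working it through.** The plan states no figure to reproduce. The check is a comparison of the sections, followed by an illustration with assumed shares.

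**1. Changes permitted against changes tracked.**

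| Therapy | Section | Condition for a change | Change must be documented | In the factor |
|---|---|---|---|---|
| AEDs | 5.6 | at least 6 months stable on a ZX008 dose, good seizure control | yes | yes |
| VNS parameters | 5.6.1 | same | yes | no |
| KD | 5.6.2 | same | yes | no |

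Each section also lets changes outside these limits be discussed with the Medical Monitor.

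**2. Can AED be read to include the device and the diet?** No. It is defined as a drug, and Section 3.1, in barring new treatment, names AEDs and other antiepileptic treatments separately.

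**3. Who ends up where.** A subject with an AED change is flagged, with or without a VNS or KD change. A subject with no change is correctly unflagged. Only a subject with a VNS or KD change and no AED change is unflagged despite a change in epilepsy therapy.

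**4. Share of the unchanged group affected.** Let a be the share of subjects with an AED change and v the share with a VNS or KD change but no AED change. Neither is in the protocol. The share of the unchanged group with an unflagged change is c = v / (1 − a).

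| | v = 1% | v = 5% | v = 10% |
|---|---|---|---|
| a = 20% | 0.01/0.80 = 1.3% | 0.05/0.80 = 6.3% | 0.10/0.80 = 12.5% |
| a = 40% | 0.01/0.60 = 1.7% | 0.05/0.60 = 8.3% | 0.10/0.60 = 16.7% |

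**5. Effect on the contrast.** Let d be the true difference in outcome between changed and unchanged subjects. If a VNS or KD change moves the outcome as an AED change does, the observed contrast is d(1 − c), so it shrinks by the percentages above. If it moves the outcome equally far in the opposite direction, the contrast is d(1 + c) and grows. The documents do not say which applies.

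**6. When it can arise.** VNS and KD are held constant for at least the first 6 months, so Month 6 is the earliest point under the standing permission. That leaves at most 36 − 6 = 30 months. A subject titrated on the standard schedule to 0.8 mg/kg/day (Section 3.1) takes steps at about Days 30, 44 and 58. Six months of stability from there falls at about Month 8. Core-study subjects may also move to another extension study after at least 1 year, or to commercial product. For the Year 1 objective in Section 2.2, the exposed window is at most about 6 of 12 months.

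**The case against.** The strongest reply is that nothing is miscoded. Section 10.5.2.1 asks about AEDs and builds an AED indicator, and a subject with only a VNS or KD change is correctly recorded as having no AED change. Section 10.5 leaves the full description of analyses to the SAP, which is not shown and may widen the factor. Every subject takes at least one AED, whereas VNS and KD are optional and new antiepileptic treatments are barred, so only existing users can be affected. Section 1.1.1 says that uncontrolled studies of KD and VNS show infrequent meaningful benefit. The primary objective is safety, and this is a sensitivity analysis of a secondary endpoint.

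Most of that stands and limits the weight of the point. It does not remove the gap. The protocol itself specifies the factor, and specifies it more narrowly than its own rules on permitted changes. An SAP that followed the text would carry this forward. The clause in Section 10.5.2.1 allowing other model factors is discretionary and depends on findings in the core studies. By holding VNS and KD constant for 6 months and requiring every change to be justified, the protocol treats them as able to affect the outcome.

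Three stronger readings are tempting, and the documents do not support them.

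- A reader might infer that the check would be falsely reassuring. That needs changes that reduce seizures. Permitted changes follow good control, and relaxing a diet or lowering stimulation could raise counts.
- A reader might infer a material shift in the pooled seizure reduction. Assume that 10–30% of subjects use VNS or KD and 25–50% of those change it: 0.10 × 0.25 = 2.5% to 0.30 × 0.50 = 15% of subjects. Assume also that a change alters the on-treatment rate by 20–40%. The interim median change of −66.8% (Section 1.3) leaves about 33.2% of baseline, so the effect is 6.6 to 13.3 points per affected subject. The pooled shift is then 0.025 × 6.6 = 0.17 to 0.15 × 13.3 = 2.0 points, before allowing for the later start of changes or for overlap with AED changes. Every input except the median is assumed. Recoding the factor would in any case not move the main estimate.
- A reader might treat criterion 10j as describing the analysed subjects. It covers de novo subjects, whom the synopsis excludes from effectiveness analyses. It shows only that the protocol classes VNS and KD as interventions for epilepsy.

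**Conclusion.** The point holds as a minor one. The only specified check on background therapy covers one of the three therapies that may be altered under the same condition, so subjects with only a VNS or KD change join the unchanged group and blur the contrast.

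The conclusion that they are grouped this way rests on the text alone. The 1.3 to 16.7% range rests entirely on the assumed values of a and v. The actual number may be small, since it is confined to existing VNS or KD users without an AED change, from about Month 6 at the earliest under the standing permission. The direction of any bias is unknown, and the main ANCOVA, which has no background-therapy factor, is unaffected.

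**What to change.** In Section 10.5.2.1, and in the SAP if it repeats the narrow wording, define the factor as any change during the OLE Treatment Period in concomitant AED dose or type, VNS stimulation parameters or ketogenic diet. Widen the trigger for the follow-on exploratory analyses in the same way. Use the same definition in any analysis that cuts diary data at the first change.

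The cost is about one sentence. VNS and KD use is already recorded in the CRF, and every change must already be documented with an explanation and justification. The text does not say that the dates of VNS and KD changes are entered in the CRF, so the sponsor should confirm this before relying on them. The downside is slightly more subjects in the changed category.

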During the OLE Treatment Period, all subjects will be treated initially with 0.2 mg/kg/day for 1 month to assess effectiveness of this dose in all study subjects. After 1 month at a dose of 0.2 mg/kg/day, the investigator may adjust the dose of each subject based on effectiveness and tolerability. For subjects who are not receiving concomitant STP, including de novo subjects and those who participated in core studies ZX008-1501, ZX008-1502, and dose regimen 1 or 2 from Cohort 1 of ZX008-1504, dose changes should be made in increments of 0.2 mg/kg/day, to a maximum of 0.8 mg/kg/day but not to exceed total dose of 30 mg/day. For subjects who are receiving concomitant STP, including de novo subjects and those who participated in core study ZX008-1504 Cohort 1 dose regimen 3 and Cohort 2, and the first dose change will be to 0.4 mg/kg/day and the final dose change will be to 0.5 mg/kg/day, but not to exceed 20 mg/day. Dose increases should not occur earlier than every 14 days at each dose level. Dose increases may only occur after a review of the diary and reported AEs, and if, in the investigator's opinion, seizure frequency, severity, and/or duration indicates a change in medication regimen is warranted. Dose decreases for tolerability can occur at the investigator's discretion, in dose amounts and frequency appropriate for the situation. ZX008 dose adjustments outside of these parameters should be discussed with the Medical Monitor prior to initiation.

In addition, if a subject has been stable on the same dose of ZX008 for 6 months or longer, investigators may adjust the doses of one or more of the other concomitant AEDs as per typical clinical practice. Concomitant AEDs may be withdrawn completely but all subjects must remain on a minimum of 1 concomitant AED plus ZX008. No new concomitant AEDs or

antiepileptic treatments may be introduced while in this study. All medication dose changes must be documented with a clinical explanation and justification. Concomitant AED dose adjustments outside of these parameters should be discussed with the Medical Monitor prior to initiation.

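### The AED-change sensitivity analysis adjusts for a post-baseline indicator tied to response and time on study, so it cannot show how sensitive the key result is to AED changes

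*Protocol*

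**What the plan says.** Section 10.5.2.1 sets the purpose of the additional analysis: "to assess the sensitivity of the key effectiveness analysis to changes in dose or type of concomitant AED medications that may occur". It also fixes the method. The key analysis is run again "with a factor added to the model to indicate whether a subject had a change in prescribed dose or type of concomitant AED medication". This indicator covers the OLE Treatment Period. If AED changes appear to have a significant impact on effectiveness, more exploratory work may follow. The outcome comes from the same period: the convulsive "seizure frequency will be calculated from all available data collected during either the pre-ZX008 Baseline or OLE Treatment Periods".

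The rules on when an AED may change differ between sections.

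- **Section 5.6:** "During at least the first 6 months of the study, subjects will continue to receive their existing AEDs at the same dose" as before the study. Changes become possible "once the subject has been stable on a ZX008 dose for at least 6 months with good seizure control".
- **Section 3.1, with the same rule in the synopsis:** "if a subject has been stable on the same dose of ZX008 for 6 months or longer, investigators may adjust the doses" of other AEDs. Seizure control is not mentioned.
- **Exceptions:** Section 5.6 states that "Concomitant AED dose adjustments outside of these parameters should be discussed with the Medical Monitor prior to initiation". Section 3.1 has the same provision, and the synopsis softens it with a proviso that discussion take place if possible.

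Section 5.6 also bars new AEDs. Section 4.4 lists clinically significant worsening of seizures that calls for treatment outside the protocol as a reason for discontinuation.

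**The concern.** A covariate helps in a sensitivity analysis when the outcome does not determine it. This one is recorded after baseline, inside the outcome window, and under Section 5.6 a subject qualifies for an AED change partly by doing well. Its coefficient then mixes two things: any effect of changing AEDs, and the fact that subjects who change may already differ in response.

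The indicator also depends on time on study. A subject who leaves before 6 months on a stable dose can hardly be coded as a changer. Under Section 3.1, ZX008 dose increases are made only when seizure frequency, severity or duration warrants them, and each increase restarts the stable-dose period. Poor response therefore tends to delay eligibility even under the wording that omits seizure control.

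Seizures after an AED change stay in the outcome whether or not the factor is in the model. At stake is the only check the protocol specifies of whether AED changes drive the key effectiveness result.

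**Working it through.** The protocol gives no figure for this analysis, so there is none to reproduce. The check asks what the factor would show if AED changes had no effect on seizures at all.

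**Inputs.** From the protocol: the median change in convulsive seizure frequency of -66.8% (Section 1.3), used only to set the scale. Assumed, because the documents do not give them:

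- the log ratio of OLE to baseline frequency is normal with SD 1.0;
- good control means a reduction of at least 50%;
- 300 subjects;
- the ANCOVA is run on the log ratio with age group and log baseline;
- the AED-change probabilities are those in the table;
- where an AED effect is included, it acts on the whole-period ratio.

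**Arithmetic for the first row.** The mean log ratio is ln(1 - 0.668) = -1.103. Good control means a log ratio at or below ln 0.5 = -0.693, which is 0.409 SD above the mean. So P(good) = Φ(0.409) = 0.659, and the normal density there is 0.367. Relative to the overall mean, well-controlled subjects average -0.367/0.659 = -0.557 and the others +0.367/0.341 = +1.076.

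Suppose 40% of well-controlled subjects and none of the others change AEDs. Changers average -0.557. Non-changers consist of 0.6 × 0.659 = 0.395 well controlled and 0.341 not, so they average (0.395 × -0.557 + 0.341 × 1.076)/0.736 = +0.199. The difference is -0.756, and exp(-0.756) = 0.47. A model with no AED effect thus shows changers with 53% lower seizure frequency.

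**Simulation, 1000 runs per row, no true AED effect:**

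| Change probability, well controlled vs not | Factor ratio | p<0.05 |
|---|---|---|
| 40% vs 0% | 0.47 | 100% |
| 40% vs 10% | 0.59 | 99.5% |
| 40% vs 20% | 0.72 | 80% |
| 30% vs 30% | 1.00 | 5.5% |
| 20% vs 40% | 1.45 | 80% |

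The same arithmetic gives 0.47, 0.59, 0.72, 1.00 and 1.45, so the ratios do not rest on simulation noise.

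The adjusted mean moves too. In the first row it goes from -66.9% without the factor to -72.2% with equal weights on the two groups, and the no-change group alone reads -59.6%. Neither shift reflects an AED effect.

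**With a true 30% rise in seizures from AED change.** Each ratio is multiplied by 1.3. At 40% vs 0%, 0.47 × 1.3 = 0.61, which points the wrong way. At 40% vs 20%, 0.72 × 1.3 is about 0.94, with p<0.05 in only 8% of runs, so the real effect is masked. Only when change is unrelated to response is 1.30 recovered.

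**The case against.** A reader might infer from Section 5.6 that AED changes are confined to well-controlled subjects, and hence that the factor measures response instead of AED sensitivity and is bound to favour changers. The documents do not support that. Section 3.1 and the synopsis omit the seizure-control condition, and all three places let other changes proceed through the Medical Monitor. The wording on adjusting or altering doses also covers increases, which could occur in poorly controlled subjects. Section 10.5.2.1 counts any change, inside or outside the rule. The table shows the bias vanishing at equal change rates and reversing when changes are mostly in poorly controlled subjects. Neither its size nor its direction can be predicted from the protocol.

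Three further points count for the plan. The follow-on exploratory analyses are permitted, not triggered by a fixed rule. Keeping post-change seizures in the endpoint matches the all-available-data definition and is not an error in itself. Effectiveness is a secondary objective in a single-group safety study, and the main ANCOVA and the stratified Wilcoxon test do not use the factor.

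All of this stands and limits the point. It does not rescue the analysis: in this set-up the coefficient is unbiased only if AED change is unrelated to response, and the stable-dose requirement, the seizure-driven titration, the discontinuation rule and the Section 5.6 wording all make that implausible.

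**Conclusion.** The point holds in a limited form. The indicator is post-baseline, set within the outcome window, and confounded with response and time on study. Its coefficient and the adjusted mean therefore do not show how sensitive the key result is to AED changes. With no true AED effect the factor ratio spans about 0.47 to 1.45 over the change rates tried. A true 30% rise can read as 0.61 or as a non-significant 0.94.

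These figures illustrate the problem and do not forecast the trial's result. They rest on the assumed change rates, the 50% threshold for good control and SD 1.0 for the log ratio. The key effectiveness estimate itself is not undermined; what fails is the check on it. Separately, the AED-change rules in Section 5.6, Section 3.1 and the synopsis differ and must be reconciled.

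**What to change.** Replace the factor as the sensitivity check with two repeats of the key analysis, both reported beside the main estimate:

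1. Use each subject's OLE seizure data only up to the day before the first AED change.
2. Restrict to Day 31-180, also cut at any earlier AED change. Section 5.6 holds AEDs constant in this window apart from Medical Monitor exceptions.

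Any model with the AED-change factor can remain as a description of who changed, without being read as an AED effect. The wording on AED changes in Section 5.6, Section 3.1 and the synopsis should be reconciled.

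The cost is a wording change and two re-runs on data already collected. There are real limits. The Day 31-180 window keeps 180 - 31 + 1 = 150 of up to 1085 days, about 14% for a completer. It also includes ZX008 titration, so a difference from the main result may reflect dose or duration instead of AED changes. In the first repeat the cut date may itself depend on response, so the two should be read together.
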